participant experiences and circumstances in the ICU, parts of the intervention may be omitted or amended at the discretion of the interventionist to meet the needs of the participant. The EMPOWER intervention is designed to be administered in the ICU, but to accommodate the varying needs of participants, may be administered in other private clinical settings on the campuses of the recruiting sites as well as via applications used for telehealth, such as but not limited to Webex or Zoom.

All participants who receive EMPOWER (both open trial and RCT cases) will be audio- and/or video-recorded for supervision and training purposes, with the participant's approval. They can opt out of video-recording and still participate, but audio-recording is mandatory.

EMPOWER is based on well-established cognitive-behavioral and acceptance-based techniques that aim to reduce maladaptive avoidance of distressing emotions. The EMPOWER interventionist will be compassionate and will attempt to provide validation of the surrogate decision-makers' experience; to teach tools for remaining present-focused; to explore the surrogate decision-maker's and the patient's wishes, values, and decision challenges; to increase their sense of acceptance and permission to experience challenging emotions; and to prepare them to cope with future distressing situations.

The primary outcome will be peritraumatic distress. We hypothesize that at post-intervention assessment, surrogate decision-makers who receive EMPOWER will have significantly lower symptoms of peritraumatic distress when compared to surrogate decision-makers who receive ICU enhanced usual care.

Secondary surrogate decision-maker outcomes will be surrogate decision-maker Prolonged Grief Disorder (PGD) symptom severity (either pre-loss/anticipatory or post-loss/bereavement grief) and experiential avoidance at one-month and three-month follow up. Exploratory surrogate decision-maker outcomes will be symptom severity of PTSD, depression, anxiety, and decision regret at one-month and three-month follow up. For both secondary and exploratory outcomes, we hypothesize that surrogate decision-makers who receive EMPOWER will have significantly lower symptoms compared to surrogate decision-makers who receive ICU enhanced usual care.

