Adult Surrogate Post-intervention Assessment (T2): PG-12 (if patient is alive); FOLLOS (if patient is alive); PG-13 (if patient is deceased); ²⁴ ^{25,26} PDI; PDEQ; IES-R; BEAQ; STAI; DTS revised version; Caregiver Self-Efficacy in the ICU Scale; DRS - EMPOWER; Regret Assessment; Post-Intervention Satisfaction Questionnaire (PISQ).

Adult Surrogate 1 Month Post-T2 Assessment (T3): PG-12 (if patient is alive); FOLLOS (if patient is alive); PG-13 (if patient is deceased); PDI; IES-R; BEAQ; STAI; PHQ-9; DTS revised version; Critical Care Family Satisfaction Survey- EMPOWER; CEQUEL-R (if patient is alive); CEQUEL ²³ (if patient is deceased); Quality of Life (if patient is alive); Quality of Death (if patient is deceased); DRS - EMPOWER; Regret Assessment; Medical Information Update

Adult Surrogate 3 Months Post-T2 Assessment (T4): PG-12 (if patient is alive); FOLLOS (if patient is alive); PG-13 (if patient is deceased); PDI; IES-R; BEAQ; STAI; PHQ-9; DTS revised version; CEQUEL-R (if patient is alive); CEQUEL (if patient is now deceased, but was alive at T3); Quality of Life (if patient is alive); Quality of Death (if patient is deceased); DRS - EMPOWER; Regret Assessment; Medical Information Update; Qualitative Exit Interview for (participants receiving EMPOWER intervention only).

Pediatric Surrogate Assessments: STAI, PDI, PG-12, IES-R, DRS-EMPOWER at all 4 timepoints, with brief demographics at T1, Post-Intervention Satisfaction Questionnaire at T2, and Qualitative Exit Interview at T4 (for participants receiving EMPOWER intervention only).

Measure Title	Time Points Used*	Description of Measure
McGill Quality of Life Scale	Screener	Items 5 through 8 are used to measure anxiety/depression.
Partner Dependency Scale (PDS)	Screener	Items 1 and 2 of the PDS are used to measure dependency. The language is altered to refer to the patient rather than a spouse.
Columbia Suicide Severity Rating Scale	Screener	Items 1 and 2 of the CSSRS are used to measure suicidal ideation.
Peritraumatic Distress Inventory (PDI) ICU Version	T1, T2, T3, T4	Measures peritraumatic distress.
Peritraumatic Dissociative Experiences Questionnaire (PDEQ) ICU Version	T1, T2	Measures experiences of dissociation that may occur in the ICU. Instructions are changed to prompt the participant to specifically answer the survey in reference to their experience in the ICU.
Impact of ICU Events Scale- Revised (IES-R)	T1, T2, T3, T4	Measures symptoms of PTSD.

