6.1 Data Analysis Plan

Below are descriptions of the statistical procedures performed to test each of the hypotheses. Participant data will be stored in a locked file cabinet and using a secured REDCap database. Missing data will be estimated using a multiple imputation procedure described by Schafer and Olsen³⁷. There will not be a data monitoring committee due to the trial's relatively short duration and the minimal risks the intervention poses. Trial data will

not be independently audited. An interim analysis of the pilot data will occur to inform the conduct of the randomized control and edits to the EMPOWER manual. Data for participants who come bereaved before the administration of EMPOWER or EUC interventions will be treated as exploratory and analyzed separately.

Specific Aim #1: Develop EMPOWER for surrogate decision-makers of critically ill patients who at risk of becoming unable to communicate and/or are currently are unable to communicate in the ICU.

There are no hypotheses for this aim. We will use thematic content analysis, a well-established, systematic qualitative analysis approach in health research, to identify themes from stakeholder participants' narratives and exit interviews. We will follow Morse's²¹ guidelines for conducting rigorous qualitative research (e.g., audit trail, saturation) using Atlas.ti software. We will independently review each interview transcript as well as qualitative data gathered from manual edits and Delphi survey responses and will synthesize and interpret participants' feedback about the content of the EMPOWER manual.

Specific Aim #2: Determine the feasibility, tolerability, acceptability, and preliminary effects of EMPOWER on surrogate decision-maker mental health.

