We will compute descriptive statistics to characterize the feasibility and acceptability of EMPOWER by examining helpfulness/satisfaction ratings, rates of recruitment, reasons for refusal, and number of modules/booster calls completed. Targets will include completion of 4/6 modules for feasibility and tolerability. Target acceptability will be an average score greater than 3 on the acceptability items in the post-intervention satisfaction questionnaire among participants who received EMPOWER. Tolerability will also be measured by open ended-responses to qualitative questions asked at T4 regarding negative experiences, emotional difficulties, and perceived costs and benefits of participating in the intervention. Drop-out will not be considered as a metric of tolerability due to the highly stressful and variable circumstances of ICU caregiving, unless participants drop out of the study and specifically express that they consider it to be too distressing. Qualitative data analysis will be used to analyze data from open-ended questions to identify the most helpful components of EMPOWER.

To evaluate the preliminary effects of EMPOWER among participants in the combined RCT and COVID-19 open trial phases, we will use a hierarchical linear modeling (HLM) and an intent-to-treat approach. HLM is statistically appropriate because of the clustering within interventionists and within surrogate decision-makers. HLM will correct for this clustering by modeling interventionists and surrogate decision-makers as random effects, as has been done in prior trials ^{38 39}. This will also provide a treatment assignment model coefficient and effect size estimate for our future, larger study.

HLM modeling will determine differences between surrogate decision-makers and patients assigned to EMPOWER vs. enhanced usual care. The primary outcome is post-intervention (T2) differences in PDI scores. Secondary outcomes are differences in scores on the PGD 12/13 and BEAQ at one-month (T3) and three-month (T4) follow up from T2. Exploratory outcomes are differences in scores on the IES-R, STAI, PHQ-9 and Decision Regret Scale at one-month (T3) and three-month (T4) follow up. HLM models will include covariates, either as fixed-effect or time-varying, if those variables are found to be significantly statistically associated with both intervention assignment and the outcome examined.

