6.1 Statistical power and sample size considerations

The pilot RCT will enroll 60 participants (30 EMPOWER, 30 enhanced usual care). This number of participants ensures stable estimates of treatment effects and confidence intervals, and, in case the effects of EMPOWER happen to be large, adequate (~80%) statistical power to detect a minimum treatment effect size (Cohen's d) of 0.75 (at alpha=0.05).

Of note, participants from the COVID-19 open trial will be considered in this N of 60. Accounting for these participants, the projected balance between groups will be 2:1, or 40 EMPOWER participants to 20 EUC. At 80% statistical power and alpha=0.05, this assignment ratio is still sufficient to detect a minimum treatment effect size (Cohen's d) of 0.75.

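### The power statement for the 2:1 split is slightly optimistic: with 40:20, a two-sided t-test has about 77% power at d = 0.75, and 80% power needs d of about 0.78

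*Combined protocol and SAP*

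**What the plan says.** All the power statements are in section 6.1, Statistical power and sample size considerations. For the pilot RCT as designed, with 30 participants per arm, the plan claims "adequate (~80%) statistical power to detect a minimum treatment effect size (Cohen's d) of 0.75 (at alpha=0.05"). It then counts the COVID-19 open-trial participants within the same total of 60, so that "the projected balance between groups will be 2:1, or 40 EMPOWER participants to 20 EUC". For that split it states: "At 80% statistical power and alpha=0.05, this assignment ratio is still sufficient to detect a minimum treatment effect size (Cohen's d) of 0.75".

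Neither sentence names a test, its sidedness, or any allowance for loss of participants or clustering.

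Three statements in section 6.1, Data Analysis Plan, bear on what the figure assumes:

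- On participants bereaved early: "Data for participants who come bereaved before the administration of EMPOWER or EUC interventions will be treated as exploratory and analyzed separately".
- On incomplete data: "Missing data will be estimated using a multiple imputation procedure".
- On adjustment: "HLM models will include covariates, either as fixed-effect or time-varying, if those variables are found to be significantly statistically associated with both intervention assignment" and also with the outcome.

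The primary outcome is the PDI score at T2. The model is a hierarchical linear model with random effects for interventionists and surrogates.

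**The concern.** The plan attaches the same minimum detectable effect, d = 0.75 at 80% power and alpha 0.05, to two allocations of the same 60 people. In a two-group comparison with a common variance and a fixed total, moving from 1:1 to 2:1 always loses precision. Both sentences can be true only if the 30:30 design has enough spare power to absorb that loss. The second sentence also drops the approximation sign that the first one carries.

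The pilot is meant to supply effect estimates for a larger trial, and a reader faced with a null or borderline T2 result will use this sentence to judge how sensitive the comparison was. As written, it suggests that the change of ratio has no cost for the detectable effect. It also hides what the figure depends on: the test used, and whether all 60 contribute to the primary comparison.

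**Working it through.** **Inputs.** From the power section: alpha = 0.05, d = 0.75, target power 80%, allocations 30:30 and 40:20, total 60. Not stated, so inferred: a two-sample t-test, two-sided. No allowance is made for loss, clustering or baseline adjustment, because the section mentions none.

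**Formula.** With n₁ and n₂ per arm, the noncentrality is λ = d·√(n₁n₂/(n₁+n₂)) on n₁+n₂−2 = 58 degrees of freedom. Power is the probability that a noncentral t variable exceeds the two-sided 5% critical value, 2.002.

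**Step 1: reproduce the plan's 30:30 figure.** λ = 0.75 × √(900/60) = 0.75 × 3.873 = 2.905. Power is 81.5%, and 80% power is reached at d = 0.736. This fits the plan's approximate 80%.

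**Step 2: same test, 40:20.** λ = 0.75 × √(800/60) = 0.75 × 3.651 = 2.739. Power is 76.8%, and 80% power needs d = 0.780.

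**Step 3: cross-check by relative efficiency.** 4 × 40 × 20 / 60² = 0.889, so the standard error grows by 1/√0.889 = 1.061. Scaling the 30:30 detectable effect gives 0.736 × 1.061 = 0.781, which agrees with step 2 within rounding.

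**Step 4: other readings of the unstated test.** Normal approximation: power = Φ(λ − 1.960), and d for 80% power = (1.960 + 0.842)/√(n₁n₂/(n₁+n₂)). For 40:20 this is Φ(0.779) = 78.2% and 2.8016/3.6515 = 0.767.

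| Test at alpha 0.05 | 30:30 power at d = 0.75 | d for 80% | 40:20 power at d = 0.75 | d for 80% |
|---|---|---|---|---|
| Two-sided t | 81.5% | 0.736 | 76.8% | 0.780 |
| Two-sided normal | 82.8% | 0.723 | 78.2% | 0.767 |
| One-sided t | 89.0% | 0.650 | 85.6% | 0.689 |

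Only the one-sided row supports the 40:20 sentence, and it does not fit the 30:30 sentence. Of the three, the two-sided t-test is closest to the plan's own figure.

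**Step 5: what would hold d = 0.75 at 80%.** At 2:1, the two-sided t-test needs 44:22, a total of 66 (power 80.8%). This gives a sense of scale only; it is not a recommendation.

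**Step 6: sensitivity to inputs the documents do not give.** These are assumptions.

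- *Separate analysis of the early bereaved.* If 3 of the 60 were bereaved before delivery and the ratio held (38:19), power at d = 0.75 would be 74.6% and the detectable effect 0.80. With 6 of 60 (36:18) these become 72.2% and 0.82.
- *Adjustment for baseline PDI.* Dividing d by √(1 − r²), with 57 degrees of freedom, a T1–T2 correlation r of 0.3 gives 80.6% for 40:20, and 0.5 gives 87.5%. Power reaches 80% at r of about 0.28.

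**The case against.** The arithmetic is not in dispute; the case on the other side is about weight and framing.

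*The gap is trivial in a pilot.* It is 2 to 3 points of power. The plan justifies 60 participants first by stable estimates and mentions power only in case the effect is large. The 40:20 split is itself a projection: at the same total, 36:24 would give 79.9% and 42:18 would give 74.5%. All of this is fair, and it is why no design change follows. It does not make the sentence correct, since that sentence names 40:20 and states 80% without the approximation sign.

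*The two-sided t-test is inferred, and the hypothesis is directional*: EMPOWER surrogates "will have significantly lower symptoms of peritraumatic distress when compared to surrogate decision-makers who receive ICU enhanced usual care". It is an inference. But no one-sided test is stated anywhere, and a one-sided test would make the 30:30 figure 89.0%.

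*Saying a ratio is still sufficient does not say that power is unchanged.* True: 30:30 had a little to spare. The spare was too small, however, and giving the same minimum effect for both splits does present the change as free.

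*The planned model may do better than a t-test.* This is the strongest point. The "Peritraumatic Distress Inventory (PDI) ICU Version" is collected at T1, and a modest baseline correlation would restore 80%. But the power section claims no adjustment, the analysis plan enters covariates only conditionally, and it does not say that T1 enters as a repeated measure. Clustering by interventionist could pull the other way. The documents therefore do not settle power under the planned model, and the 77% belongs to an unadjusted t-test.

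**Conclusion.** The 40:20 statement does not hold on the basis that reproduces the plan's 30:30 figure. With an unadjusted two-sided 5% t-test and all 60 analysed, power at d = 0.75 is 76.8% rather than 80%, and the effect detectable with 80% power is 0.780 rather than 0.75. Moving from 30:30 to 40:20 costs 81.5 − 76.8 = 4.7 points. The normal approximation narrows the shortfall but does not remove it.

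The size is small and the effect estimate is untouched by it. The conclusion rests on a two-sided test, which is inferred from the plan's figure, and on no adjustment for baseline. The bereavement and correlation scenarios show direction only; the conclusion does not depend on them. This is a correction that should be made because the stated figure is wrong and cheap to put right. It does not call the design into question.

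**What to change.** Replace the last sentence of the power section with wording such as:

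> With 40:20 evaluable, an unadjusted two-sided t-test at alpha = 0.05 has about 77% power for d = 0.75 and 80% power for d = 0.78. This assumes that all 60 are in the primary analysis; participants bereaved before EMPOWER or EUC are analysed separately, and no allowance is made for missing T2 data or interventionist clustering.

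If the team wants to show a loss scenario or a baseline-adjusted figure, the assumed loss or correlation should be labelled as an assumption. A baseline-adjusted figure should be quoted only if the analysis plan also commits to that adjustment.

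The cost is two sentences. Enrolment, data collection and analysis stay as they are; the stated detectable effect moves from 0.75 to 0.78.
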